### 6.2.4.3 Cortical Basal Ganglia Functional Scale (CBFS)

The CBFS is a novel rating scale that evaluates experiences in daily living (EDL) and behavioral, language, and cognitive impairments in subjects with 4 repeat tauopathies (Lang et. al., 2020). The CBFS consists of 14 questions on motor EDLs and 17 questions on non-motor EDLs, each of which is rated on a Likert 5-point scale that rates function from 0 to 4, where 0 = normal or no problems and 4 = severe problems. The questions are for the subject but should be answered by the subject and caregiver working together. Responses are to be based on the usual or average function over the past 2 weeks.

The Total scores for the Motor Experiences, Non-Motor Experiences, and Overall will be summarized.

#### 6.2.4.3.1 CBFS Motor Experiences of Daily Living (CBFS-M)

The CBFS-M Assesses how motor symptoms impact daily activities. The CBFS-M is calculated by summing (adding) the scores from 14 items.

If all 14 items are answered, the formula for the CBFS-M is a simple sum:

$$CBFSm_{Total} = \sum_{i=1}^{14} X_i$$

If only one (<10% of data) of 14 motor EDLs is missing, the available item mean multiplied by 14 will be used.

$$CBFSm_{Total\_Adj} = \left( \frac{\sum X_i}{N_{Answered}} \right) \times 14$$

Where:

- $X_i$  = individual motor-related item scores (from 0 to 4)
- $N_{Answered}$  = number of motor-related items with a valid response
- 14 = total number of items in the full CBFS-M score
- Range of the score is 0 to 56

If 2 or more of the 14 items are missing, the total CBFS-M score will be set to missing.

#### 6.2.4.3.2 CBFS Non-Motor Experiences of Daily Living (CBFS-NM)

The CBFS-NM evaluates cognitive, emotional, and autonomic dysfunction. The CBFS-NM is calculated by summing (adding) the scores from 17 items.

If all 17 items are answered, the formula for the CBFS-NM is a simple sum:

$$CBFSnm_{Total} = \sum_{j=1}^{17} X_j$$

If only one (<10% of data) of 17 non-motor EDLs is missing, the available item mean multiplied by 17 will be used.

$$CBFSnm_{Total\_Adj} = \left( \frac{\sum X_j}{N_{Answered}} \right) \times 17$$

Where:

- $X_j$  = individual non-motor related item scores (from 0 to 4)
- $N_{Answered}$  = number of non-motor-related items with a valid response
- 17 = total number of items in the full CBFS-NM score
- Range of the score is 0 to 68

If 2 or more of the 17 items are missing, the total CBFS-NM score will be set to missing.

#### 6.2.4.3.3 CBFS Total Score (Overall Functional Impact)

The CBFS Total Score (overall functional impact) is the sum of the motor and non-motor components.

$$CBFS_{Total} = \sum_{i=1}^{14} X_i + \sum_{j=1}^{17} X_j$$

To ensure that the total CBFS is a sum of the CBFS-M and CBFS-NM, the available item mean is used separately by the number of items missed in each component.

$$CBFS_{Total\_Adj} = \left[ \left( \frac{\sum X_i}{N_{Answered}} \right) \times 14 \right] + \left[ \left( \frac{\sum X_j}{N_{Answered}} \right) \times 17 \right]$$

- $X_i$  = individual motor-related item scores (from 0 to 4)
- $X_j$  = individual non-motor related item scores (from 0 to 4)
- $N_{Answered}$  = number of items with a valid response

- 14 = total number of items in the full CBFS-M score
- 17 = total number of items in the full CBFS-NM score
- Range of score is 0 to 124

The CBFS will be completed at Screening/Baseline and at Months 6, 12, 18, 24, 30 and 36/ET.

## **6.2.5 Motor Assessments**

Motor assessments will be shown for the Ambulatory Population.

### **6.2.5.1 2-Minute Walk Test (2MWT)**

The 2MWT is a measure of self-paced walking ability and functional capacity, particularly for individuals who cannot manage longer periods of walking. The 2MWT has been used as an outcome measure in a variety of health conditions, including neuromuscular diseases in the adult and pediatric populations. The test measures the distance a person can walk in 2 minutes. Individuals are encouraged to walk as fast as they can, safely, for 2 minutes, and to cover as much ground as possible without running. Rest breaks are allowed, if needed, but the timer is not stopped. Walking aids can be used, if needed, but should be kept consistent from test to test. Rest breaks and use of aids should be recorded. As normal subjects aged <59 years can walk up to 200 meters in 2 minutes, a testing area that allows a minimum number of turns should be available.

The 2MWT will be done at Screening/Baseline and at Months 6, 12, 18, 24, 30, and 36/ET.

2MWT distances exceeding 300 meters will be excluded from analyses as these values are implausible for this study population (Bohannon, 2017).

### **6.2.5.2 Timed Up and Go (TUG)**

The TUG is used to determine the time (in seconds) needed to progress from sitting to standing and walking. In addition, the test helps to evaluate the probability for falls. The TUG, which was initially designed for elderly persons, is also used in populations with conditions that can affect ambulation and balance. This tool is validated for populations with Parkinson's disease, multiple sclerosis, hip fracture, Alzheimer's disease, cerebrovascular accident (CVA), Huntington's disease, and post-CVA. The individual starts in a seated position in a chair with armrests and, upon command, stands up, walks 3 meters, turns around, walks back to the chair, and sits down. The time stops when the subject is seated. The use of walking aids should be recorded and kept consistent between tests.

The TUG will be done at Screening/Baseline and at Months 6, 12, 18, 24, 30, and 36/ET.

## **6.2.6 Severity of Illness Scales**

### **6.2.6.1 Clinical Global Impression – Severity of Illness (CGI-S)**

The CGI-S scale is a 1-item 7-point scale that requires the clinician to rate the severity of the patient's illness at the time of the assessment relative to the clinician's past experience with patients who have the same diagnosis. Raters select one response based on the following question: "Considering your total clinical experience with this particular population, how ill is the patient at this time?" Scores are as follows: 1 = normal, not at all ill; 2 = borderline ill; 3 = mildly ill; 4 = moderately ill; 5 = markedly ill; 6 = severely ill; and 7 = among the most extremely ill patients.

The CGI-S will be completed at Screening/Baseline.

### **6.2.6.2 Clinical Global Impression - Change (CGI-C)**

The CGI-C is a 1-item 7-point scale that requires the clinician to assess how much the patient's illness has improved or worsened relative to the baseline state at the beginning of the intervention. Raters select one response based on the following question, "Compared to your patient's condition at the beginning of study, how much has your patient changed?" Scores are as follows: 1 = very much improved; 2 = much improved; 3 = minimally improved; 4 = no change; 5 = minimally worse; 6 = much worse; and 7 = very much worse.

The CGI-C will be completed at Months 6, 12, 18, 24, 30, and 36/ET.

### **6.2.6.3 Patient Global Impression – Severity of Illness (PGI-S)**

The PGI-S is a 1-item questionnaire that is designed to assess a patient's impression of disease severity (Guy, 1976). It may be interpreted as the patient-reported outcome counterpoint to the CGI-S, which is assessed by a clinician. The PGI-S item asks subjects to describe their current symptoms on the following 4-point scale: 1 = normal, 2 = mild, 3 = moderate, or 4 = severe.

The PGI-S will be completed at Screening/Baseline.

### **6.2.6.4 Patient Global Impression - Change (PGI-C)**

The PGI-C is a 1-item measure used to assess a patient's perception of overall improvement or worsening in response to treatment. It may be interpreted as the patient-reported outcome counterpoint to the CGI-C. The qualitative assessment of meaningful change is determined by the patient in response to the question, "Compared to your condition at the beginning of study, how much has your condition changed?" Scores are as follows: 1 = very much improved; 2 = much improved; 3 = minimally improved; 4 = no change; 5 = minimally worse; 6 = much worse; and 7 = very much worse.

The PGI-C will be completed at Months 6, 12, 18, 24, 30, and 36/ET.

## 6.2.7 Functional, Psychiatric and Other Assessments

The assessments described in this section are only completed if the subject has a study partner who has provided informed consent for the study. Results will be shown for the Caregiver Population.

### 6.2.7.1 Functional Activities Questionnaire (FAQ)

The FAQ is a 10-item questionnaire that measures instrumental activities of daily living, such as preparing balanced meals and managing personal finances. Functional changes in instrumental activities of daily living that require a higher cognitive ability are noted earlier in the dementia process than changes in basic activities of daily living. Therefore, the FAQ is useful to monitor these functional changes over time in subjects with mild dementia and has been used in clinical trials of subjects with mild cognitive impairment and in subjects with mild to moderate and severe dementias.

The FAQ assesses 10 functions related to personal finances, shopping, playing games, meal preparation, watching television, following the news, taking medications, and traveling. Each function is rated from 0 to 3 (0 = normal, 1 = has difficulty but can do alone, 2 = requires assistant, and 3 = totally dependent on others to do). The FAQ demonstrates high correlation with cognitive measures and is sensitive to change over time.

A total FAQ score is calculated by summing (adding) the scores of 10 items together.

If all 10 items are answered, the formula for the FAQ is a simple sum:

$$FAQ_{Total} = \sum_{i=1}^{10} X_i$$

If only one (10% of the data) FAQ item is missing, the available item mean multiplied by 10 will be used.

$$FAQ_{Total\_Adj} = \left( \frac{\sum X_i}{N_{Answered}} \right) \times 10$$

Where:

- $X_i$  = individual item scores (from 0 to 3)
- $N_{Answered}$  = number of items with a valid response
- 10 = total number of FAQ items
- Range of the score is 0 to 30

If 2 or more of the 10 items are missing, the total FAQ ( $FAQ_{Total}$  and  $FAQ_{Total\_Adj}$ ) will be set to missing. To reduce bias due to missing data,  $FAQ_{Total\_Adj}$  will serve as the primary variable for reporting on the FAQ, and  $FAQ_{Total}$  will be included in the ADaM datasets for future sensitivity analyses beyond the scope of this SAP.

The FAQ will be completed at Screening/Baseline and at Months 6, 12, 18, 24, 30 and 36/ET.

### **6.2.7.2 Neuropsychiatric Inventory – 12 Item Version (NPI-12)**

The NPI-12 is a 12-item inventory that provides a brief assessment of neuropsychiatric symptomatology in clinical practice settings and in clinical trials. The NPI-12 assesses the following 12 behavioral domains that are common in dementia: hallucinations, delusions, agitation/aggression, dysphoria/depression, anxiety, irritability, disinhibition, euphoria, apathy, aberrant motor behavior, sleep and nighttime behavior change, and appetite and eating change.

The NPI-12 is administered by the clinician to the caregiver. The caregiver is usually a family member who is involved in the daily care of the subjects but can be administered to a professional caregiver or other involved person as long as the person has detailed knowledge of the patient's behavior. The clinician reads each question to the caregiver as it is written. After reading the screening question, the caregiver is asked if the behavior that was described is present, if the answer is "no" then the clinician proceeds to the next section and reads the next screening question. If the answer is "yes" to the screening question, the rater then rates the frequency (rarely, sometimes, often, very often), severity of the symptoms that have been present within the last month (mild, moderate, or severe), and the associated impact of the symptom manifestations on them (i.e., caregiver distress; not at all, minimally, mildly, moderately, severely, or very severely or extremely). The total scores can be used for monitoring the worsening of or improvement in neuropsychiatric symptoms.

Each of the 12 NPI domain items are rated on:

- Frequency (*F*): 1 (Rarely) to 4 (Very Often)
- Severity (*S*): 1 (Mild) to 3 (Severe)
- Caregiver distress rating (*D*): 0 (Not at all) to 5 (Very Severely or Extremely)

The NPI-12 will be completed at Screening/Baseline and at Months 6, 12, 18, 24, 30, and 36/ET.

#### **6.2.7.2.1 NPI Total**

The NPI-12 Total score quantifies the severity and frequency of neuropsychiatric symptoms across 12 domains.

If all 12 frequency and severity items are answered, the NPI-12 Total is calculated by summing the severity x frequency scores for each of the 12 domains:

$$NPI12_{Total} = \sum_{i=1}^{12} (F_i \times S_i)$$

If one frequency item and/or one severity item are missing, the available item mean multiplied by 12 will be used:

$$NPI12_{Total\_Adj} = \left( \frac{\sum F_i \times S_i}{N_{Answered}} \right) \times 12$$

Where:

- $F_i$  = Frequency of symptom for domain  $i$  (scored 1-4)
- $Si$  = Severity of symptom for domain  $i$  (scored 1-3)
- $i$  = Each of the 12 NPI domains
- $N_{Answered}$  = Number of non-missing domains
- 12 = total number of domains
- Range of the score is 0 to 144

If 2 or more of the any frequency or severity items are missing, the NPI Total scores ( $NPI12_{Total}$  and  $NPI12_{Total\_Adj}$ ) will be set to missing. To reduce bias due to missing data,  $NPI12_{Total\_Adj}$  will serve as the primary variable for reporting on the NPI12 Total, and  $NPI12_{Total}$  will be included in the ADaM datasets for future sensitivity analyses beyond the scope of this SAP.

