#### **4.3.2.4 Other Functional and Psychiatric Assessments (Caregiver Population)**

- Change from Baseline to Months 6, 12, 18, 24, 30, and 36 in the FAQ Score
- Change from Baseline to Months 6, 12, 18, 24, 30, and 36 in the NPI-12 Total Score
- Change from Baseline to Months 6, 12, 18, 24, 30, and 36 in the CBFS Motor, Non-motor, and Total Score
- Change from Baseline to Months 6, 12, 18, 24, 30, and 36 in the Total ZBI Score

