#### 6.2.7.2.2 NPI-12 Distress Total

The NPI-12 Distress Total score measures how distressing each symptom is to the caregiver, rated from 0 to 5 for each domain.

If all 12 distress items are answered, the NPI-12 Distress Total is calculated by summing the caregiver distress ratings:

$$NPI12_{Distress} = \sum_{i=1}^{12} (D_i)$$

If distress item is missing, the available item mean multiplied by 12 will be used:

$$NPI12_{Distress\_Adj} = \left( \frac{\sum D_i}{N_{Answered}} \right) \times 12$$

Where:

- $D_i$  = Caregiver distress score for domain  $i$  (scored 0-5)
- $i$  = Each of the 12 NPI domains
- $N_{Answered}$  = Number of non-missing domains
- 12 = total number of domains
- Range of the score is 0 to 60

If more than 1 of the distress items are missing, the NPI Distress Total score ( $NPI12_{Distress}$  and  $NPI12_{Distress\_Adj}$ ) will be set to missing. To reduce bias due to missing data,  $NPI12_{Distress\_Adj}$  will serve as the primary variable for reporting on the NPI12 Distress Total, and  $NPI12_{Distress}$  will be included in the ADaM datasets for future sensitivity analyses beyond the scope of this SAP.

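### For an NPI-12 domain known to be present, the SAP fills a missing frequency or severity from all domains, including absent ones, so the adjusted Total is too low on average, and 0 when it is the only symptom

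*SAP*

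**What the plan says.** SAP 6.2.7.2 describes a skip pattern. After a 'no' to a domain's screening question, "then the clinician proceeds to the next section and reads the next screening question". Only after a 'yes' "to the screening question, the rater then rates the frequency", the severity and the caregiver's distress. F is scored 1 to 4 and S 1 to 3, neither with a zero category; distress is scored 0 to 5. Protocol 8.3.4.2 describes the same pattern.

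SAP 6.2.7.2.1 defines the Total as the sum of F × S over 12 domains, with a range of 0 to 144. For incomplete forms: "If one frequency item and/or one severity item are missing, the available item mean multiplied by 12 will be used". The divisor of that mean is the "Number of non-missing domains". With two or more F or S items missing, the Total is set to missing. The adjusted Total is the main reporting variable, on the stated ground of limiting missing-data bias.

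SAP 6.2.7.2.2 treats distress alike: "If distress item is missing, the available item mean multiplied by 12 will be used".

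The endpoint affected, in SAP 4.3.2.4, is "Change from Baseline to Months 6, 12, 18, 24, 30, and 36 in the NPI-12 Total Score".

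**The concern.** Multiplying an available-item mean up to the full scale is reasonable when every item is put to every respondent, as in the FAQ and the Zarit interview. The NPI-12 is different, because F and S are asked only about symptoms that are present. If one of the pair is recorded and the other is blank, the domain was screened 'yes' and its product is at least the recorded value. The rule drops the domain, ignores what was recorded, and substitutes the mean of the other 11 domains, most of which may be zeros from a 'no'.

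The adjustment therefore tends to add the kind of bias it is meant to limit. For a single subject, an incomplete form at follow-up tends to look like improvement, and one at baseline tends to exaggerate later worsening. In the extreme case, a subject with one recorded symptom is scored as having none.

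**Working it through.** **1. The SAP's range, and what it implies.** Maximum = 12 × 4 × 3 = 144, as stated. If all 12 domains had to carry ratings, the minimum would be 12 × 1 × 1 = 12. The stated minimum of 0 is reachable only if a 'no' domain counts as answered with score 0. The rest uses that reading.

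**2. The SAP rule with one incomplete domain.** Let k domains be present, one of them lacking F or S. Eleven domains are non-missing, of which k-1 are present and 12-k score 0.

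Adjusted Total = (sum of F × S over the other k-1 present domains) / 11 × 12.

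If the incomplete domain is exchangeable with the other present ones, with mean product m:

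- true mean = k·m
- mean adjusted Total = 12(k-1)m/11
- ratio = (12/11)(k-1)/k
- shortfall = k·m - 12(k-1)m/11 = m(12-k)/11

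The ratio does not depend on m. It reaches 1 only at k = 12.

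**3. Numbers.** For points and proportions, assume F uniform on 1 to 4 and S uniform on 1 to 3 (an assumption; the documents give no distribution). Then m = 2.5 × 2 = 5. Below the minimum means below the lowest Total compatible with the recorded answers: the other domains plus F × 1 if S is missing, or plus 1 × S if F is missing.

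| k | Adjusted / true (mean) | Mean true | Mean adjusted | Shortfall | Below minimum, S missing | Below minimum, F missing | Records overstated |
|---|---|---|---|---|---|---|---|
| 1 | 0% | 5 | 0 | 5.0 | 100% | 100% | 0% |
| 2 | 55% | 10 | 5.5 | 4.5 | 98% | 97% | 1% |
| 3 | 73% | 15 | 10.9 | 4.1 | 90% | 86% | 3% |
| 4 | 82% | 20 | 16.4 | 3.6 | 77% | 70% | 8% |
| 6 | 91% | 30 | 27.3 | 2.7 | 55% | 40% | 21% |

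**4. Three single records.**

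- One symptom, S recorded, F blank: adjusted Total = 0/11 × 12 = 0. The true value lies between S and 4S: 1 to 4, 2 to 8 or 3 to 12 for S = 1, 2 or 3. This needs no distributional assumption.
- Three symptoms: (F 2, S 2), (F 3, S 2) and (F blank, S 2; true F 3). True Total = 4 + 6 + 6 = 16. SAP rule: 10/11 × 12 = 10.9. The lowest compatible Total is 4 + 6 + 1 × 2 = 12, so 10.9 is impossible given the answers.
- Overstatement: five domains at 12 and a sixth truly at 1. SAP rule: 60/11 × 12 = 65.5, against a true 61.

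**5. Filling only the missing component.** In the three-symptom record, the subject's mean F over the other present domains is (2 + 3)/2 = 2.5. The Total becomes 4 + 6 + 2.5 × 2 = 15.0, against 16. Under the uniform assumption this rule averages 10, 15 and 20 at k = 2, 3 and 4, equal to the true means.

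**6. Distress.** Distress is also rated only after a 'yes'. If 'no' domains count as 0, the same ratio applies on average. However, 0 is a valid rating for a present symptom, so an adjusted Distress Total need not conflict with the recorded answers. For the same reason the stated 0 to 60 range does not itself show how a 'no' is coded.

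**7. Two sentences that collide.** If one domain lacks both F and S, the 'and/or' wording says to impute. Two items are then missing, so the next rule says to set the Total to missing.

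**The case against.** The strongest reply is that the SAP never says how a 'no' domain is coded. Read literally, unasked items are missing, the two-or-more rule voids the Total, and nothing is understated. That reading cannot be meant: any subject with a single absent symptom would have no Total, and a score of 0 could never occur. The coding should still be written down.

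The second reply is materiality, and it largely stands. The affected record is narrow: a clinician-administered domain screened 'yes' with exactly one of two ratings blank. No rate is given. NPI-12 is not among the repeated-measures outcomes in SAP 4.3.4 or the correlation endpoints in 4.4. With 30 to 60 records at a visit (assumed), one record short by 5 points moves the mean by 5/60 = 0.08 to 5/30 = 0.17 points.

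A reader might infer more than the documents support:

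- That every affected Total is too low. The bias is an average; the 65.5 against 61 record goes the other way, and at k = 6 about 21% of records are overstated under the uniform assumption.
- That the Distress Total also falls below a logical floor. It does not, because distress can truly be 0, and Distress is not a listed endpoint.
- That group trends or the external-control comparison are distorted. Nothing in the documents shows that such records are common, or that NPI-12 enters that comparison.

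**Conclusion.** The rule is wrong as written for one type of record: a domain screened 'yes' with only F or only S missing. There it discards known information and understates the Total on average for every k below 12, most severely for subjects with few symptoms. At k = 1 the result is always 0 and always wrong.

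The average ratio rests on two things: that a 'no' scores 0, which the stated range requires, and that the incomplete domain is exchangeable with the subject's other present domains. The point shortfalls and the below-minimum and overstatement percentages rest in addition on uniform F and S, and are illustrative. The all-domain mean remains reasonable when the screening question itself went unanswered, because presence is then unknown.

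The probable effect on group summaries is small. The case for changing the rule is that it can produce impossible scores in the variable chosen for reporting, and that correcting it is cheap.

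**What to change.** In SAP 6.2.7.2.1:

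- State that a domain screened 'no' scores 0 and counts as answered.
- For a domain screened 'yes' with only F or only S missing, keep the recorded component and multiply it by the subject's mean of the missing component over the other domains screened 'yes' at that visit. Do not rescale by 12/N_Answered.
- If no other domain was screened 'yes', set the Total to missing, or use a study-level mean specified in advance; do not report 0.
- Use the available-domain mean × 12 only when the screening question was not answered.
- Reconcile the 'and/or' imputation sentence with the two-or-more rule, and say what happens when a 'yes' domain has both components blank.

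In SAP 6.2.7.2.2, state how a 'no' is scored, and fill a missing distress rating for a 'yes' domain from the subject's other 'yes' domains.

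The cost is a few sentences and a small change to the NPI-12 derivations, with no change to the assessment. Distinguishing a 'no' from an unanswered screen requires the screening answer to be held in the data; the documents do not confirm this, so check it first. A count of affected records by visit would show whether the change matters in practice.

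### Does the NPI-12 Total need a stated score for domains screened 'no' and a reworded missing-item limit?

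*SAP*

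**What the plan says.** SAP 6.2.7.2 describes the interview. Each of the 12 domains opens with a screening question. After a 'no', "then the clinician proceeds to the next section and reads the next screening question"; after a 'yes', frequency (F, 1 to 4), severity (S, 1 to 3) and caregiver distress (D, 0 to 5) are rated. Protocol 8.3.4.2 describes the same procedure.

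SAP 6.2.7.2.1 then sets out the total:

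- Plain sum of F × S: "If all 12 frequency and severity items are answered".
- Proration: "If one frequency item and/or one severity item are missing, the available item mean multiplied by 12 will be used". The mean is taken over N_Answered, defined as "Number of non-missing domains".
- Total withheld: "If 2 or more of the any frequency or severity items are missing, the NPI Total scores" are set to missing.
- "Range of the score is 0 to 144".

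The neighbouring scores use simpler limits. The FAQ rule begins "If 2 or more of the 10 items are missing, the total FAQ", and the distress rule begins "If more than 1 of the distress items are missing, the NPI Distress Total score". Each has one rating per item or domain.

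**The concern.** Two things look wrong.

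The first is the unscored 'no'. The F and S scales have no zero, the plain sum asks for all 12 pairs, and a skipped pair has no value. A programmer who treats skipped ratings as missing would withhold the total from anyone with two or more 'no' domains. Those are the least affected subjects: Protocol 5.1 (criterion 12) admits prodromal subjects with no ALSP-related signs or symptoms, and SAP 4.3.2 presents results by subgroup. The loss would therefore not be random.

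The second is the missing-item limit. One F item plus one S item missing is two items. The proration sentence covers that case, but the withholding sentence, if it pools the two item types, removes the total. The limit is also counted in items while the denominator is counted in domains. Two forms with the same N_Answered could then be handled differently.

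**Working it through.** **Inputs.** F from 1 to 4, S from 1 to 3 and 12 domains (SAP 6.2.7.2); range 0 to 144 and the proration formula (ΣF×S / N_Answered) × 12 (SAP 6.2.7.2.1). The example ratings and 'yes' probabilities below are illustrative assumptions.

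**1. The stated range**

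- Maximum: 12 × 4 × 3 = 144, as stated.
- Minimum if all 12 domains are rated: 12 × 1 × 1 = 12, not 0.
- Minimum if one 'no' domain is treated as missing and prorated: (11 × 1 / 11) × 12 = 12.
- Minimum if 'no' scores 0: 12 × 0 = 0, as stated.

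So if 'no' is treated as missing, every available total is at least 12. The lower limit of 0 is reproduced only when 'no' contributes 0 and the domain counts as answered.

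**2. What the competing readings of 'no' would give**

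- Eleven domains at F = 2, S = 2 and one 'no'. With 'no' = 0: 11 × 4 = 44. With 'no' missing and prorated: (44 / 11) × 12 = 48. With 'no' missing and F and S items pooled (two items): no total.
- Twelve 'no' answers. With 'no' = 0: total 0. With 'no' missing: no total.
- Share of forms with at least two 'no' domains, if each domain is independently 'yes' with probability 0.1, 0.3, 0.5, 0.7 or 0.9: about 1.00, 1.00, 0.997, 0.915 or 0.341.

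The last line shows that the literal reading would leave the table nearly empty over most of that range. That is good evidence that it is not the intended reading.

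**3. The missing-item limit, with 'no' = 0**

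Classify forms by missing F items (0, 1, 2+) and missing S items (0, 1, 2+), which gives nine cells.

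| Missing F, missing S | Counted by type | Pooled |
|---|---|---|
| 0, 0 | plain sum | plain sum |
| 1, 0 or 0, 1 | prorate | prorate |
| 1, 1 | prorate | proration and withholding sentences conflict |
| other five cells | no total | no total |

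Only one cell depends on the reading. Counting by type removes the conflict. Pooling cancels the 'and' half of the proration sentence.

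**4. Size within that cell**

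Take four 'yes' domains at F = 2, S = 2 and eight 'no' domains. The complete total is 4 × 4 = 16.

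- F and S missing in the same 'yes' domain: (12 / 11) × 12 = 13.1.
- F missing in one 'yes' domain and S in another: (8 / 10) × 12 = 9.6, taking a part-rated domain as missing for N_Answered, since its product cannot be formed.
- F missing in two domains, also N_Answered = 10: no total on either reading.

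The last two lines are the difference in units. It is uneven, but it can be computed without ambiguity once items are counted by type.

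**5. Distress**

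D starts at 0 and 12 × 5 = 60, so the range of 0 to 60 in SAP 6.2.7.2.2 holds. With one rating per domain, the unit question does not arise.

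**The case for a change.** The best case for a change is that a range line is not a derivation rule. SAP 1 makes the SAP the governing document for analyses, SAP 4.1.11 says that missing data on specific scales is dealt with in the Appendix, and SAP 4.1.3 calls for independent verification by separate programming. Two programmers should not have to infer a score from a range. One sentence would settle it, and V2.0 was itself issued partly to add detail on derived variables.

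Part of this stands. The convention for 'no' is not written in either document, the withholding sentence is clumsy, and nothing says that a domain with only F or only S missing leaves N_Answered. Stating these things would be tidier.

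The rest does not stand. SAP 4.1.11 speaks of data that could not be obtained; a screening 'no' was asked for and obtained. SAP 1 refers to the CRFs for data collection, and Protocol 8.3 to a separate assessment manual. Neither is available here, and either may already record 'no' as 0. Separate programming also makes it unlikely that totals lost for most mildly affected subjects would go unnoticed.

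The FAQ comparison is weak, because the FAQ has one rating per function and the NPI-12 total needs two per domain. An item limit with a domain mean is a workable choice. Counting missing domains instead would change a pre-specified rule, withholding some totals that are now prorated, with no evident gain.

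**Conclusion.** No change follows. The text leaves an unwritten convention that analysts would fill in one sensible way: a domain screened 'no' scores 0 and counts as answered, and the limit of two is applied to frequency items and to severity items separately. That reading reproduces the stated range and reconciles both missing-item sentences.

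Under it, added wording would change no total. Even if items were pooled, one of nine missing-data cells would be affected, at a frequency the documents do not give. The reach is small: the NPI-12 Total is summarised at baseline (SAP 4.2.2) and descriptively over time in the Caregiver Population (SAP 4.3.2 and 4.3.2.4). It is outside the models named in SAP 4.3.4 and the correlation endpoints in SAP 4.4, in a study that SAP 4.1.6 calls exploratory. The Distress Total is not among the endpoints listed in SAP 4.3.2.4.

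This rests on two assumptions: that 'no' is stored or derived as 0, and that a part-rated domain is treated as missing in N_Answered. The first is strongly implied by the range; the second follows from the product needing both ratings.
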